4.13.13. Measures of potential mediators

Measures of potential mediators including; knowledge, intention and beliefs about consequences, derived from the intervention logic model will also be collected. Specific questions developed will be asked to track changes in behaviour and patient activation using the PREMIUM Abbreviated Activation Scale (PAAS) (62), a 5-item scale, adapted from the Behavioural Activation for Depression Scale (BADS-SF) (63). PAAS includes five indicators of behavioural activation assessed on a scale of 0 ('not at all) to 5 ('yes, completely') for a total continuous score of 25.

4.13.14. Comorbidities and medications

The self-report by the participants, adapted by the STEPs module for NCDs (64) will be used for confirmation of any medically-diagnosed history of raised blood pressure, heart disease, hypercholesterolemia, stroke, lung diseases and treatment advised by a health worker for these diseases will be collected. Self-report of any medically-diagnosed history of communicable/infectious diseases e.g. hepatitis B, C, Dengue, COVID-19, Tuberculosis, Malaria, Chikungunya and HIV will be recorded.

4.13.15. Blood tests

For all the consenting participants a blood sample (5-6 ml) will be drawn at the study site after recruitment at baseline for the biochemical assessment, following a standardized protocol for each study site for the tests including Hb, WBC, renal function tests including serum urea, serum creatinine and eGFR, lipid function test including triglycerides, total cholesterol, HDL, LDL, Thyroid function tests including T3, T4, TSH, RBS and Liver function test including only serum ALT. However, at the 3rd month as well as on 6thmonth follow-up (only 2 ml blood) will be drawn from the consenting participants for the Glycated haemoglobin (HbA1c) test. All the tests will be performed from standardized laboratories for each site.

OUTCOMES	Scales	Baseline	Month 3	Month 6
Demographics	Adapted from WHO STEPwise approach to Surveillance (STEPs) instrument, Version 3.2	Х		
Physical body measurements (Weight, height, Body Mass Index, waist circumference, hip circumference, waist–	WHO STEPS surveillance manual for measurements	х		х

Table 1. Outcomes with scales and measurement schedule

OUTCOMES	Scales	Baseline	Month 3	Month 6
hip ratio, and blood pressure)				
Blood tests: Haemoglobin level (Hb), white blood cell count (WBC), renal function tests including serum urea, serum creatinine and estimated Glomerular Filtration Rate (eGFR), lipid function test including triglycerides, total cholesterol, high-Density Lipoprotein cholesterol (HDL), low-Density Lipoprotein cholesterol (LDL), Thyroid function tests including (serum triiodothyronine (T3), Thyroxine test (T4), Thyroid-stimulating hormone (TSH), Random blood sugar (RBS), and Liver function test including only serum Alanine Transaminase.		X		
Blood test: Glycosylated haemoglobin (HbA1c)		Х	х	x
Comorbidities	Adapted from the STEPs module for non-communicable diseases and communicable/infectious diseases	X		Х
Caseness and severity of depression	Physical health questionnaire (PHQ-9)	Х	x	х
Anxiety	Generalized Depression and Anxiety (GAD-7)	Х		x

OUTCOMES	Scales	Baseline	Month 3	Month 6
Diabetes distress	Problem Areas in Diabetes Scale - 5 (PAID-5)	х		х
Self-efficacy	Diabetes Empowerment Scale- Short form (DES-SF)	Х		х
Diabetes self-management and self-care	Perceived Diabetes Self- Management Scale (PDSMS) Summary of self-care diabetes activities scale (SDSCA)	x		x
Health risk behaviour: Physical activity	International Physical Activity Questionnaires (IPAQ, (short version)	х		х
Health risk behaviour: Tobacco use	An adapted version of The STEPs tobacco and smokeless tobacco modules.	х		х
Health risk behaviour: Alcohol use	Adapted questions of the STEPs alcohol module.	Х		х
Diabetes complications	A set of questions in DiaDeM CRF on Diabetes-related microvascular and macrovascular complications.	х		х
Health-related quality of life (HRQoL)	EQ5D-5L including visual analogue scale (EQ-5d-VAS)	Х	х	х
Mediators	A set of questions in DiaDeM-CRF for potential mediators including; Knowledge about depression/symptoms and regarding the link between behaviour and depression, intention to plan and regularly do healthy activities, beliefs about consequences, derived from the intervention logic model	X	X	Х

OUTCOMES	Scales	Baseline	Month 3	Month 6
Changes in avoidance and activation over the course of Behavioral Activation for depression	PREMIUM Abbreviated Activation Scale (PAAS)	х	х	х
Economic outcomes: 1. Employment Status 2. Household status 3. Productivity Loss (income and days (hours) of work lost) 4. Out-Of-Pocket Payments (OOP) 5. Opportunity Cost of Time (average wage and time) 6. Borrowing / Selling Assets 7. Household earnings and Expenditure 8. Catastrophic Health Spending (OOP as % of household expenditure)	Set of questions related to economics outcomes in DiaDeM CRF adapted from Asset index questionnaire	X		X
Health care resource use	Modified client service receipt Inventory (CSRI)	х		х
Medication	Modified client service receipt Inventory (CSRI)	х		х

4.14. Data collection and entry

[figure not shown]
RAs recruited for the DiaDeM programme at six study sites in Bangladesh and Pakistan will screen, recruit and randomise participants, and collect baseline information. The RAs who will collect information for three months and six months follow-ups for an individual participant shall be different from those who will recruit, randomize and collect baseline information to ensure blinding. Apart from being good clinical practice (GCP) certified, the RAs will receive one week's training on trial procedures including taking informed consent, administering and completing the questionnaires/scales, recording and reporting the data, in hard copies as well as electronically in tablets, qualtrics and in all study logs. They will also be trained on ethical issues such as autonomy of individual participants on making decisions about participation, freedom to withdraw from the trial without giving any reason or consequence, privacy, confidentiality, anonymity etc. The staff involved in the trial will be trained on data protection processes. The staff will be strictly monitored to ensure compliance with privacy standards.

Data will be entered in paper format for the screening and blood test reports whereas the CRFs will be entered directly into an online survey tool (Qualtrics), a secure and password-protected resource available at the University of York. Collected data will be stored on a central database server.

PAGE 19

The trial scheme diagram is given below:

Figure 1. Trial Flow Diagram

4.15.Statistical analysis

The following outcomes will be calculated: number of eligible patients; the proportion of eligible patients approached for consent; the proportion of eligible patients not approached and reasons why; the proportion of patients approached who provide consent; the proportion of patients approached who do not provide consent; the proportion of patients the proportion of patients providing consent who are randomised; the proportion

of patients randomised who do not receive the randomly allocated treatment; the proportion of patients dropping out between randomisation and follow-up. A CONSORT diagram will be provided to display the flow of participants through the study. Data from the clinical outcome measures will be summarized descriptively by study arm and by severity (mild and moderate/severe): continuous data using mean, standard deviation, median and 25th and 75th percentiles; categorical data using a number of events and percentages. The recruitment rate and 95% confidence interval (CI) will be estimated. Completion rates of all the outcome measures will be reported by the study arm and by severity (mild and moderate/severe). The number of sessions attended and completed will also be reported.

5. PROCESS EVALUATION

A mixed-methods process evaluation will be embedded within the feasibility trial, focusing on what was delivered, how the delivery was achieved and how context might affect the delivery of the intervention in order to inform plans for the full trial and future scale-up. The process evaluation will follow the Medical Research Council guidance for process evaluation. (65)

Quantitative data on attendance, drop-out and delivery will be gathered as part of the feasibility trial and will be important in assessing the dose, reach and delivery of the intervention. Questions about the mediators identified in the logic model (Knowledge about depression/symptoms and regarding the link between behaviour and depression, intention to plan and regularly do healthy activities, beliefs about consequences, derived from the intervention logic model) will be collected at baseline and follow-up (table 1). Quantitative data on delivery and receipt of intervention components will be collected(65–68) checking against adherence criteria, using a pre-designed proforma or checklist which will check the extent to which components of the intervention have been delivered and patient responsiveness. Random sessions will be recorded with consent and researchers will be able to complete the proforma accordingly, this will provide information on the fidelity of the intervention and patient receptiveness.

Semi-structured interviews and possibly focus groups will be conducted in each site with patients, facilitators, supervisors and managers (approximately N=12 patients; N=12 facilitators; N=8 managers/supervisors) immediately following the intervention. The interviews may include storytelling techniques and/or photovoice to facilitate discussion. The qualitative data will explore experiences of intervention delivery and acceptability, identify any barriers and drivers to delivery including contextual factors such as the health facility environment or any other factors that may affect delivery and implementation. Unintended consequences of the intervention, mechanisms of change, perceptions on task shifting and staff training needs will also be explored during the different interviews. The process evaluation will help us understand how the intervention that work well and those that do not. This information will help us to adapt the intervention further for the full trial.

To support the quality of reporting and assessment of intervention fidelity, a description of the core components of an intervention is required, (65) Informed by adherence criteria (68) developed during BA development and adaptation phase and the feasibility study, we will develop a framework to measure adherence, exposure, delivery and participant responsiveness for use in the definitive trial.

6. ECONOMIC EVALUATION

We will test methods of collecting service use and other economic data for the economic analysis of the trial (WS4). Methods to be considered include patient self-report using an adapted Client Service Receipt Inventory (66) and health services data. We will check the appropriateness and the completeness of the questions. DiaDeM Resource use questionnaire (Modified client service receipt inventory CSRI) will be used for health care resource use and medications for the last six months period. Control variables

(household and housing information, asset index, education, ethnicity, marital status, rural/urban setting and clinical information (complications and comorbidities) will be used for the economic modelling

7. DATA MANAGEMENT

Data during the feasibility trial and its nested mixed process evaluation will be collected through researcher-administered interviews, focus groups, face-to-face assessments and observations. For process evaluation and fidelity assessment of intervention delivery, some intervention sessions will be audio-recorded, with consent. The focus group discussions (FDGs) will also be audio-recorded. The written notes taken during the FGDs by the note taker will also be in hard copies. The screening forms, consent forms and blood reports will also be captured as hard copies. All baseline and outcome data in the form of the CRFs will be captured electronically via tablets.

Qualitative interviews will be transcribed in the language of the interview and anonymized but linked with the trial ID before translation for analysis. Digital recordings of the interviews will be stored in a secure, password-protected folder. Once the analysis of the interviews will be completed all the recorded versions will be erased from the digital recorders.

The researchers will ensure the anonymity and confidentiality of the participants, restricting any kind of access to non-authorized persons. Participants will be assigned unique study IDs which will be used for all tools and records so that no identifiable information is accessible to non-authorized persons. Every identifiable information of the participants will be stored at each study site securely; electronic records will be kept under password protection and hard copies will be stored in locked filing cabinets.

Encrypted data transfer between the study sites and the University of York will be via secure Drop-off services available through the University of York. All files transported in this manner should be encrypted as zip files using a strong password consisting of at least 8 characters with numbers, a mix of letters in lower and upper case, and punctuation or other symbols. Data received through this method should only be accessed on desktop computers or laptops which are connected to an encrypted server.

For non-sensitive or non-confidential data, researchers should share the data through the DiaDeM team drive on the Google Drive cloud-based storage platform, or through the University of York drop off service (https://dropoff.york.ac.uk/).

In accordance with the University of York Research Data Management Policy, all anonymised research data, which underpin published results or have a long-term value will be retained for 10 years after the completion of activities. Upon completion of the DiaDeM activities, all non-anonymised data will be destroyed.

8. DATA MONITORING

Data will be monitored for quality and completeness by a delegated trial manager at the study sites, followed by a second check by the study data lead at the University of York using verification, validation and checking processes. The data management policy of DiaDeM formulated under the guidance of the University of York Trials Unit's guidance regarding processes for data monitoring will be followed by all the research team.

Data will be reported to the Independent Trial Steering Committee (ITSC) and Data Monitoring and Ethics Committee (DMEC) as required.

9. ETHICAL CONSIDERATIONS

Formal ethical approvals have been acquired from the Health Sciences Research Governance Committee (HSRGC), University of York (Ref: HSRGC/2020/409/B), Diabetic Association of Bangladesh (Ref: BADAS-ERC/EC/20/00300), National Bioethics Committee Pakistan (Ref: No.4-87/NBC-578/20/ 1101), Institutional Research and Ethics Forum of Rawalpindi Medical University (Ref:242/IREF/RMU/2020) and Ethics Committee of Office of Research Innovation & Commercialization (ORIC), Khyber Medical University (KMU), Pakistan on 08/10/2020. (Ref: DIR/KMU/UEC/25).

The local Principal Investigator from each study site will be responsible for ensuring that all ethical principles are strictly followed and also ensuring that the study procedures and protocols are being stringently adhered to. They will be responsible for the correspondence with the local ethics bodies and to submit applications for the approval of extensions and amendments in the protocol. The study will follow international standards for the ethical conduct of research and comply with the governance regulations and requirements in force at each site and country.

The study will adhere to the fundamental principles of human rights and dignity laid down in the Declaration of Helsinki. Study procedures will comply with legislation and guidance for good practise governing the participation in research of people lacking capacity as set out in the Mental Health Act (UK) 2005.

Written informed consent, the anonymity of participants and the right of withdrawal will be followed by the research teams. The reports of the biochemical blood tests and findings of the physical measurements will be shared with the participants. For the participants, who screen positive on tests for depression or anxiety, routine usual care pathways and referral systems will be followed. In case of any comorbidity detected during the study based on the biochemical assessment or any other screening tests/scales, they will be referred to the relevant medical department, as indicated. If the answer to question 9 of the PHQ-9 scale indicates a risk of self-harm, the suicide risk pathway developed for each study site will be followed.

10. ADVERSE EVENTS

All the specific procedures and guidelines regarding the adverse event assessment, reporting and notifications as given below will be followed:

10.1. Description of potential adverse events

There is no pharmacological intervention involved and the behavioral activation also poses no risk since it will consist of only motivational support. Therefore, it is improbable that any adverse events (AEs) would be related to the context or delivery of the intervention. There are very low risks related to the study procedures like drawing of the blood samples, taking physical measurements and administration of scales, inquiring about the lifestyles, risk, mental and physical health or their management, etc.

However, any diabetes emergencies like hypoglycemia, diabetic ketoacidosis (DKA) and hyperosmolar hyperglycemic state (HHS) deterioration of renal function leading to chronic kidney diseases (CKD) in known renal disease patients, serious diabetes complications like angina, myocardial infarction, stroke, transient lschemic attacks, diabetic foot, gangrene, limb, foot or toe amputations will be included in the list of potential AEs.

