4.1. Study groups

4.1.1. DiaDeM intervention

All participants will receive the DiaDeM intervention. Core components include: i) A structured individual therapy, BA.

ii) Delivery by non-mental health specialist staff based in diabetes services, referred to as BA facilitators, hereafter.

- iii) Supported by a treatment manual and materials, and
- iv) Supervision by a mental health specialist, referred to as BA supervisors, hereafter.

BA therapy will comprise 4-6 individual sessions, over a period of 6-12 weeks. The duration of each session may vary from person to person but usually would be 30 to 40 minutes per session.

The DiaDeM intervention is designed for face-to-face delivery or to be delivered remotely (telephone or online e.g. Whatsapp, Skype, Messenger, Zoom), or in combination. It will be delivered by facilitators, using a range of materials in lay language.

BA facilitators will be selected and then trained, from non-mental health specialist staff working in diabetes services at study sites, and BA supervisors will be mental health specialists available to supervise the intervention as part of their routine work.

In addition, the 'optimised usual care' leaflet, describing depression, its treatment with details of how to access help, will also be offered to the intervention group.

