10.3. Adverse event monitoring

AEs will be assessed not only by the non-mental health specialists but also by the consulting clinical staff of the diabetes centre, at each contact/visit/session with the study participant, irrespective of the trial arm, in accordance with the adverse AE review checklist. They will immediately inform the RAs about any observed AEs and or those reported by the study participant, who will record them and their potential association with study interventions or procedures will also be determined. Serious adverse events will be defined according to International Conference on Harmonisation of technical requirements for registration of pharmaceuticals for human use-Good Clinical Practice (ICH GCP) and will be reported to the respective country coordinating centres according to the agreed timelines.

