10.4. Adverse event reporting and notifications

Expected AE/SAEs: Not Reportable

- 1. Poor control of blood glucose levels
- 2. Hypoglycemia which is self-treated and not severe
- 3. Rising serum creatinine levels/worsening kidney function
- 4. Raised liver enzyme ALT levels.
- 5. Development of less serious/non-debilitating diabetes complications- retinopathy, neuropathy, diabetic foot.

Expected AEs/SAEs: Standard Reporting

- 1. Diabetes emergencies such as repeated hypoglycemia, hypoglycemia leading to hospitalization/unconsciousness, diabetic ketoacidosis (DKA) and hyperosmolar hyperglycemic state (HHS)
- 2. Deterioration of renal function leading to chronic kidney diseases (CKD) or worsening of stages of CKD in patients who initially had a diagnosis of renal disease at recruitment.
- 3. More serious complications of diabetes leading to heart disease (angina, MI), stroke, TIAs, diabetic foot leading to gangrene/ limb amputations.

Unexpected and Related SAEs

These events will require Expedited Reporting. All unexpected SAEs judged to be related to the trial, occurring from the date of the consent up to study end must be recorded on the Related/Unexpected Serious Adverse Event Form and sent to the Programme Manager. The original form should also be posted/emailed to the University of York Trials Unit in real-time and a copy retained on site. For each Related/Unexpected SAE the following information will be collected:

- Date of SAE
- Full details in medical terms with a diagnosis, if possible
- Duration (start and end dates; times, if applicable)
- Action taken
- Outcome

Any follow-up information should be sent to the University of York Trials unit as soon as it is available. Events will be followed up until the event has been resolved or a final outcome has been reached. All Unexpected/Related SAEs will be reviewed by the Chief Investigator and subject to expedited reporting to the Sponsor and the main REC by the Programme Manager on behalf of the Chief Investigator within 15 days.

Participants with SAEs must be followed up until clinical recovery is complete (including laboratory results returning to normal or baseline if relevant), or until the event has stabilised with proper information entered in the 'Follow-up report'

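### Section 10.1 calls behavioural activation free of risk, and no text makes a suicide-risk pathway activation at follow-up an adverse event or brings it to the DMEC

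*Protocol*

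**What the plan says.** On the risk of the intervention, protocol section 10.1 states that "the behavioral activation also poses no risk since it will consist of only motivational support" and concludes that adverse events related to it are improbable. Section 4.1.1 introduces the intervention differently: "Core components include: i) A structured individual therapy, BA". Section 5 adds that "Unintended consequences of the intervention, mechanisms of change, perceptions on task shifting and staff training needs will also be explored" in the process evaluation interviews.

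On suicidality, section 9 provides: "If the answer to question 9 of the PHQ-9 scale indicates a risk of self-harm, the suicide risk pathway" of the site is followed. Section 4.13.2 and Table 1 schedule the PHQ-9 at baseline, 3 months and 6 months, in both arms.

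On adverse events:
- Section 10.3 has facility and clinical staff assess them "at each contact/visit/session with the study participant, irrespective of the trial arm, in accordance with the adverse AE review checklist". The research assistants (RAs) record what is observed or reported.
- Serious events by the ICH GCP definition "will be reported to the respective country coordinating centres according to the agreed timelines".
- Section 10.4 has three tiers: expected and not reportable; "Expected AEs/SAEs: Standard Reporting"; and expedited reporting for "All unexpected SAEs judged to be related to the trial".
- Section 12.3 asks the DMEC to appraise adverse events. Section 11 makes their frequent occurrence a ground for stopping.

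**The concern.** The trial enrols only people with confirmed depression, and section 9 plans for the possibility that some will be at risk of self-harm. The safety section does not follow this through. It begins by declaring the therapy harmless, names only somatic events, and does not connect the question 9 pathway to the adverse event record.

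Two things are at stake. First, the relatedness of a serious event decides whether it is expedited, and section 10.1 tells the assessor beforehand that a related event is improbable. Second, question 9 is a suicidality measure scheduled alike in both arms. If pathway activations do not become adverse events, the DMEC can review adverse events, and the stopping guidance can be applied, without the safety signal most specific to this population.

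**Working it through.** No figure in the plan has to be reproduced. The check sets sections side by side and counts.

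**1. Nature of the intervention.** Section 10.1 rests its no-risk claim on the intervention being motivational support only. Section 4.1.1 makes a structured therapy its first core component, and section 5 sets out to look for unintended effects. The premise in 10.1 does not match the intervention described elsewhere.

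**2. Relatedness.** Under 10.4, expedited reporting requires an event that is serious, unexpected and judged related. Section 10.1 calls relatedness improbable. The no-risk sentence therefore bears on the judgement that opens the expedited route.

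**3. Events named.**
- Section 10.1: hypoglycaemia, DKA, HHS, renal deterioration to CKD, angina, myocardial infarction, stroke, TIA, diabetic foot, gangrene, amputation = 11 examples. Psychiatric: 0. The total depends on how the list is split; the zero does not.
- Section 10.4: 5 not reportable + 3 standard reporting = 8 items. Psychiatric: 0.
- By comparison, 10.4 classifies raised ALT and rising creatinine, which Table 1 schedules at baseline only. The PHQ-9 is scheduled at all three time points.

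**4. Tracing two cases through the text.**

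| Step | New, non-serious ideation found by question 9 at 3 months | Serious self-harm |
|---|---|---|
| Section 9 | Site pathway, if the answer indicates risk | Pathway applies only if question 9 shows risk |
| 10.2 exemption | Does not apply (new or worse) | Does not apply (new or worse) |
| 10.3 | Recorded if someone treats it as an adverse event; no text says that they must | Recorded; reported as an SAE whatever its relatedness |
| 10.4 | Fits none of the three tiers | Expedited only if judged related and unexpected |
| DMEC | Sees it only if it was recorded as an adverse event | Sees it within its general remit |

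The break is at 10.3 in the first column: the pathway is activated, but the record does not have to follow.

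**5. Volume of question 9 answers after randomisation.** Inputs: 128 participants, 64 per arm, two follow-up visits, and the 80% follow-up rate in section 4.5.
- Both arms: 128 × 2 × 0.80 = 204.8, about 205. At full follow-up: 128 × 2 = 256.
- Per arm: 64 × 2 × 0.80 = 102.4, about 102. At full follow-up: 64 × 2 = 128.

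The share of these that will activate the pathway, newly or at a worse level, cannot be derived from the protocol.

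**The case against.** The strongest reply is that the general machinery already covers this. Section 10.3 has RAs record any adverse event observed or reported, in both arms. Section 10.2 exempts a baseline condition only if it does not worsen. SAEs go to the coordinating centres regardless of relatedness, and the DMEC reviews adverse events. Item-level triggers would normally sit in the adverse event checklist and the site pathways, which are not shown. All of this stands. A reader might infer that the plan bars the recording of suicidality, leaves serious self-harm unreported or leaves patients unprotected; the text supports none of these. The unseen checklist cannot, however, correct the statement in 10.1 or add an item to 10.4.

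A second reply is that falling outside the 10.4 tiers is not special to suicidality. Of the four combinations of serious or non-serious with related or unrelated, 10.4 covers one for an unlisted event, and 10.3 with 10.4 covers two. The same holds for a faint at a blood draw. This is correct, so those fractions do not measure the gap. What is specific here is that the protocol itself foresees the event and measures it on schedule, but names it nowhere in the safety section.

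Third, one might infer that reporting will be biased between arms, because section 4.1.2 gives controls no further study contact with the non-specialist staff. That is possible but unproven: clinical staff assess both arms.

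Fourth, making every rise on question 9 an adverse event would go beyond the protocol's own trigger, an answer that indicates a risk of self-harm, and would feed item fluctuation into the stopping guidance. That objection is accepted, and the fix keeps the existing trigger.

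**Conclusion.** The point holds as a gap in safety recording and oversight. The no-risk sentence conflicts with the protocol's own account of the therapy and prejudges relatedness. No named event in 10.1 or 10.4 is psychiatric in a trial of confirmed depression. No text makes a pathway activation at follow-up an adverse event or brings it to the DMEC.

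The size is modest. The site pathway still protects the individual, general recording and SAE routes exist, and no feasibility outcome, progression criterion or estimate changes. The conclusion concerns the protocol text alone; if the checklist or site pathways already require an adverse event record, the recording gap narrows, but the wording of 10.1 and the lists in 10.1 and 10.4 still need correction.

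**What to change.** - **10.1:** replace the no-risk claim with a statement that the therapy is expected to pose low risk. Name new or worse suicidal ideation, self-harm and suicide attempt as potential adverse events.
- **10.4:** list these for standard reporting whatever the judged relatedness. Because that tier is headed as expected events, state that a serious event judged related still goes through expedited reporting.
- **10.3:** state that any activation of the site suicide-risk pathway at 3 or 6 months that is new or worse than at baseline is recorded as an adverse event by the follow-up RA, in both arms. Use the existing trigger in section 9, not any one-point rise on question 9.
- **DMEC:** supply descriptive counts by arm, with the arm added by the statistician so that the follow-up RA stays blinded.

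The cost is wording in three subsections and one table, with no new visit or questionnaire. There will be some extra adverse event forms, in a number that the protocol does not allow to be derived. The counts are likely to be low and can only be descriptive. The clinical pathway itself is unchanged.
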